10.2 Management of missing, unused or spurious data

If data are missing, illegible or incoherent, requests for further information will be sent to the investigator in question. Although every effort will be made to ensure that each patient's data is complete, some patients may not have data on one or more measures.

For the intention-to treat analysis the missing data will be imputed. The imputation method will depend on whether the missing data are at baseline or follow-up visit as well as the reason for the missing data as further described below.

Missing baseline data for patients will be imputed. For missing data in any of the measurements which are taken again at the second baseline, these values might be used in place of the first baseline measurement. Evaluation whether other missing baseline data might not be missing at random, will be done by exploring patterns of missing data within different measurements and patients for which data was collected.

Strong evidence for missing data patterns within measurements of secondary interest may lead to the exclusion of such measurements for any supportive analysis and will be documented in the study

ottobock.	CLINICAL INVESTIGATION PLAN	Document number:	PD-PS00120016A-001
		Version number:	7
Project name	Clinical trial comparing C-Brace to KAFO/SCO	Project no.	PS00120016A

report accordingly. In case such a pattern is observed within the measurement of primary interest may lead to the study being declared invalid in regard to the analysis planned for it.

Appropriate data management as defined in the protocol should reduce the chance of this being the case. Strong evidence for missing data patterns within patients of specific characteristics will be evaluated and might be indicative of a serious limitation to the study and could potentially lead to the study being declared invalid. Previous studies on the topic have not shown this to be very likely in the patients that fulfill the inclusion criteria of the study. Where data is assumed to be missing at random multiple imputation and a sensitivity analyses will be used.

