In order to perform a sensitivity analysis, patients who terminated treatment early, will be imputed using multiple imputation methods in order to substitute missing values. Here, multiple copies of the original dataset will be generated by replacing missing values using e.g. a multivariate normal distribution. Each of these complete sets will be analyzed as complete sets and the corresponding parameter and standard error estimates will be combined with taking the uncertainty of the imputation process into account.

For the patients missing follow-up data, proportions of missingness, type of missing measurements, patient characteristics and baseline value levels will be explored in order to detect patterns of missing data. If data is assumed to be missing at random the following imputation strategy will be used.

A linear mixed effects model with the outcome measure as dependent variable will be fitted to the data. This model will use the treatment group and period as fixed factor and the first baseline measure as covariate. Random patient effects will be introduced for the intercepts and thus taking the correlation within patients into account. The analysis implicitly uses a weighted average to estimate the outcome measures, with estimations coming from the complete observations and from the observations with missing values.

Missing data for study patients at follow-up on C-Brace, KAFO/SCO or both because they 1) died, 2) are lost to follow-up (LTFU), 3) withdrew from the study or were withdrawn from the study by the investigator, 4) miss the follow-up visit or 5) do not complete the outcome measure at follow-up, will be imputed by using a mixed model with a random intercept for patient and treatment group as predictor variables.

The details of the imputations methods applied will be documented in the study report.

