10.3 Planned statistical analysis

In general, the most suitable statistical analysis consistent with the form of data will be used and the underlying assumptions of the statistical method will be verified through appropriate pre-tests.

ottobock.	CLINICAL INVESTIGATION PLAN	Document number:	PD-PS00120016A-001
		Version number:	7
Project name	Clinical trial comparing C-Brace to KAFO/SCO	Project no.	PS00120016A

The analysis will be performed on the intention-to-treat (ITT) population and then on the per-protocol (PP) population. The ITT population is defined as all the patients randomized into their randomization group, regardless of the treatment received or their outcome in the study. The PP population is defined as all the patients in the ITT population without any major protocol deviations

For the outcomes measures being evaluated, three assessments are undertaken:

after base line measurements with original orthosis (first baseline measurement)

after first follow up measurement with the C-Brace or original orthosis

after second follow-up measurement with the C-Brace or original orthosis

Quantitative variables will be summarized using standard descriptive statistics (average, standard deviation, median, minimum and maximum, first and third quartile). Qualitative variables will be described using group sizes and frequencies. When relevant, 95%confidence intervals will be given.

Patient characteristics at enrolment will be presented and compared in each group to ensure the groups are initially comparable. The features of any patients lost to follow-up will be studied and influence the imputation strategy as described in 10.2.

Patient profile plots for the outcome measures in both treatment groups for all three assessments will be viewed, showing imputed values. Furthermore, the group means in each treatment group will be evaluated. Outcome measures will be visualized for the crossover periods in scatter plots of first follow up measurement against second follow-up measurement in both treatment groups i.e. period vs period plots.

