10.3.2 Primary efficacy outcome

One null-hypothesis as outlined in section 10.1 will be tested in the confirmatory analysis.

Absolute values and changes from first baseline and follow ups respectively will be presented for the Berg Balance Scale after 3 months of treatment using descriptive summary statistics for each treatment period. Moreover, percentage changes from baseline and follow ups respectively will be displayed.

The confirmatory inferential statistical evaluation of the primary outcome measure will be based on a linear mixed effects model with the Berg Balance Scale as dependent variable. This model will use the treatment group and period as fixed factor and the first baseline Berg Balance Scale as covariate. Random patient effects will be introduced for the intercepts and thus taking the correlation within patients into account.

ottobock.	CLINICAL INVESTIGATION PLAN	Document number:	PD-PS00120016A-001
		Version number:	7
Project name	Clinical trial comparing C-Brace to KAFO/SCO	Project no.	PS00120016A

The confirmatory analysis of the primary efficacy endpoint will be done for the intention-to-treat population. Additional efficacy analyses will be conducted for the per-protocol population. The p-values of these analyses will be interpreted in the exploratory sense only.

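### Section 10.2 handles missing follow-up BBS in the ITT analysis in two ways without precedence; the closing rule, read literally, omits period

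*Combined protocol and SAP*

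**What the plan says.** Section 10.3.2 (Primary efficacy outcome) makes the ITT analysis confirmatory and bases it on a linear mixed model: "This model will use the treatment group and period as fixed factor and the first baseline Berg Balance Scale as covariate", with random patient intercepts.

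Section 10.2 sets a general requirement: "For the intention-to treat analysis the missing data will be imputed". It adds that the method will depend on the visit type and on why the value is missing. For follow-up values it then gives two accounts:

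- First account: "If data is assumed to be missing at random the following imputation strategy will be used". A mixed model with random patient intercepts follows: "This model will use the treatment group and period as fixed factor and the first baseline measure as covariate". A further sentence describes estimation that draws on complete and incomplete observations.
- Closing rule: values missing through death, loss to follow-up, withdrawal, a missed visit or an uncompleted measure "will be imputed by using a mixed model with a random intercept for patient and treatment group as predictor variables".

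Multiple imputation appears twice, once without a stated role ("Where data is assumed to be missing at random multiple imputation and a sensitivity analyses will be used") and once with one ("In order to perform a sensitivity analysis, patients who terminated treatment early, will be imputed using multiple imputation methods"). Section 10.3 adds: "Patient profile plots for the outcome measures in both treatment groups for all three assessments will be viewed, showing imputed values". Section 10.2 leaves the details to the study report.

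**The concern.** The five reasons cover nearly every way in which a follow-up BBS value can be missing, so the reason does not separate the two accounts. The closing rule does not repeat the missing-at-random condition, and no sentence ranks one account above the other. A programmer who took the closing rule at its word would predict missing values from a model without period and then analyse them with a model that contains it.

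In a two-period crossover that matters when the periods differ and one sequence loses more second visits than the other. The documents establish neither condition. They do show that the sequences differ in schedule: only C-Brace-first has the 4-week wash-out (7.3.8), and participation is 8 or 9 months depending on the order (9.2). Unequal loss is therefore conceivable.

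A second question is independent of the model terms: whether follow-up values are filled in once, multiply imputed, or not filled in because the model is fitted to what was observed. The choice changes the width of the interval. If it is left to the study report, the estimate and interval depend on a decision made after the data are in.

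**Working it through.** **1. Terms side by side**

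| | Treatment | Period | First baseline | Patient intercept |
|---|---|---|---|---|
| Confirmatory model (10.3.2) | yes | yes | yes | yes |
| First account (10.2) | yes | yes | yes | yes |
| Closing rule (10.2) | yes | not named | not named | yes |

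**2. The plan's own figures**

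The plan gives no figure for this point, but its sample size sets the scale. With p_disc = p_diff = 0.1333, one-sided α 0.05 and power 0.8 (10.1.2):

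n = [(1.645·√0.1333 + 0.842·√(0.1333 − 0.1333²)) / 0.1333]² = 44.24, and 44.24 / 0.8 = 55.3, so 56. This reproduces the plan. At its 20% dropout rate, 0.2 × 56 = 11.2, so about 11 patients miss a visit.

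Other inputs from 10.1.1: device effect 6.6429, SD of the paired difference 4.9085. Assumed here: 28 patients per sequence, all losses in period 2, between-patient SD 3 to 9, period effect π of 1 to 3 points, and the split of losses.

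**3. Shift by hand**

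The device effect is half the difference between the two sequences' mean change from period 1 to period 2. A second-period value predicted without a period term misses roughly π. With L_C losses in C-Brace-first and L_K in KAFO/SCO-first:

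shift ≈ ½·π·(L_C/28 − L_K/28) = π·(L_C − L_K)/56.

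For π = 2 and 8:3: 2 × 5/56 = 0.18. For 6:5: 2 × 1/56 = 0.036.

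**4. Shift by simulation**

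The comparison is between REML on the observed data and a fill-in by the closing rule followed by the confirmatory model, on the same simulated trials (6,000 per setting). Entries are BBS points over the range of between-patient SD.

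| Losses L_C:L_K | π = 1 | π = 2 | π = 3 |
|---|---|---|---|
| 6:5 | 0.02 | 0.03–0.05 | 0.04–0.06 |
| 7:4 | 0.05–0.06 | 0.09–0.12 | 0.12–0.18 |
| 8:3 | 0.08–0.10 | 0.15–0.21 | 0.21–0.30 |
| 11:0 (outer bound) | 0.17–0.23 | 0.33–0.45 | 0.48–0.67 |

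The hand formula falls inside these ranges. With a positive period effect and more losses in C-Brace-first, the shift favours C-Brace; it reverses if the other sequence loses more. With equal losses it is zero. At π = 2 and 6:5 to 8:3, multiple imputation from the closing rule gives the same shift within 0.005.

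Source at π = 2 and 8:3: leaving out baseline alone shifts the estimate by at most 0.01, period alone by 0.14–0.16, both by 0.15–0.21. Period is the driver; omitting baseline as well adds a little.

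**5. Interval width (no period effect)**

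If all 56 pairs were observed, SE = 4.9085/√56 = 0.656 and the half-width is 2 × 0.656 = 1.31. With complete pairs only at 8:3 (20 and 25 pairs), SE = ½ × 4.9085 × √(1/20 + 1/25) = 0.736, half-width 1.47. A valid interval that also uses the 11 single visits should lie between these.

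| Method | Half-width | 95% coverage |
|---|---|---|
| REML on observed values | about 1.40 | 94–96% |
| Single fill-in, closing rule | 1.17–1.21 | 88–91% |
| Single fill-in, all terms | about 1.2 | 89–92% |
| Multiple imputation, all terms | 1.39–1.42 | 94–96% |

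Either single fill-in is narrower than if nobody had dropped out, because the filled-in values carry no residual scatter. The narrowing is the same with or without period, so the missing term does not cause it. Multiple imputation from the closing rule covers 94–96% when there is no period effect.

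**The case against.** The best counter-reading is loose drafting. Read in sequence, the missing-at-random condition may cover both paragraphs, and the closing one may only say to whom the mixed model just described applies. The sentence about drawing on complete and incomplete observations describes likelihood estimation, and 10.3.2 mentions no filled-in values. The profile plots in 10.3 are descriptive and do not show that the confirmatory model is fitted to imputed data. The only fill-in procedure set out operationally is multiple imputation. All of this stands as a plausible account of intent, and it limits confidence to medium. It does not remove the gap: 10.2 says ITT data will be imputed, the closing rule names different terms, and nothing states the relation. Replacement of dropouts does not help either, because the ITT population keeps every randomized patient.

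Three stronger readings are tempting and are not supported:

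- That the plan biases the result towards C-Brace. This needs a period effect and unequal losses, neither of which the documents give, and the direction depends on which sequence loses more.
- That omitting period makes the interval too narrow. The narrowing comes from single fill-in, which the plan does not specify, and it occurs equally with all terms.
- That the shift should be judged against the 3-point futility rule in 10.4. That rule concerns the observed mean change at an interim after at least 35 patients have completed; imputed values for dropouts do not enter it.

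**Conclusion.** The point holds as an unresolved ambiguity in the confirmatory method, minor to should-fix, with medium confidence.

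Followed literally, the closing rule shifts the estimate by about 0.04 points at 6:5 and 0.15–0.21 at 8:3, for a 2-point period effect with 11 of 56 second visits missing. The latter is 2–3% of 6.64 (0.15/6.6429 to 0.21/6.6429) and 0.2–0.3 of the REML standard error of about 0.70. Since 6.6429/0.70 is about 9.5 standard errors, the significance verdict is unlikely to change near the assumed effect; the reported estimate would move.

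The second gap stands apart: the section does not say how follow-up values are handled. If any single fill-in were used, even with all terms, the half-width would be about 1.2 instead of 1.4 points and coverage about 90%. This needs neither a period effect nor unequal losses, only the plan's own dropout rate and that choice of method.

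**What to change.** In 10.2, state: *The confirmatory ITT analysis fits the mixed model of the Primary efficacy outcome section (treatment, period, first baseline, random patient intercept) by REML to all observed follow-up BBS values; a patient with one follow-up visit contributes that visit.* Then:

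- delete the closing treatment-only rule, or make it repeat those terms;
- limit the general requirement to impute to baseline values and the sensitivity analysis;
- label multiple imputation, with the same terms and Rubin's rules, as the sensitivity analysis in both places where 10.2 names it.

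The cost is wording only, and the model is already the planned one. The interval is somewhat wider than with a single fill-in, and patients with no follow-up BBS enter only through the sensitivity analysis. That analysis also assumes missing at random, so it does not test the assumption.

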10.3 Planned statistical analysis

In general, the most suitable statistical analysis consistent with the form of data will be used and the underlying assumptions of the statistical method will be verified through appropriate pre-tests.

ottobock.	CLINICAL INVESTIGATION PLAN	Document number:	PD-PS00120016A-001
		Version number:	7
Project name	Clinical trial comparing C-Brace to KAFO/SCO	Project no.	PS00120016A

The analysis will be performed on the intention-to-treat (ITT) population and then on the per-protocol (PP) population. The ITT population is defined as all the patients randomized into their randomization group, regardless of the treatment received or their outcome in the study. The PP population is defined as all the patients in the ITT population without any major protocol deviations

For the outcomes measures being evaluated, three assessments are undertaken:

after base line measurements with original orthosis (first baseline measurement)

after first follow up measurement with the C-Brace or original orthosis

after second follow-up measurement with the C-Brace or original orthosis

Quantitative variables will be summarized using standard descriptive statistics (average, standard deviation, median, minimum and maximum, first and third quartile). Qualitative variables will be described using group sizes and frequencies. When relevant, 95%confidence intervals will be given.

Patient characteristics at enrolment will be presented and compared in each group to ensure the groups are initially comparable. The features of any patients lost to follow-up will be studied and influence the imputation strategy as described in 10.2.

Patient profile plots for the outcome measures in both treatment groups for all three assessments will be viewed, showing imputed values. Furthermore, the group means in each treatment group will be evaluated. Outcome measures will be visualized for the crossover periods in scatter plots of first follow up measurement against second follow-up measurement in both treatment groups i.e. period vs period plots.

10.3.1 General patient and orthosis use data

Assessments will be displayed in summary tables.

10.3.2 Primary efficacy outcome

One null-hypothesis as outlined in section 10.1 will be tested in the confirmatory analysis.

Absolute values and changes from first baseline and follow ups respectively will be presented for the Berg Balance Scale after 3 months of treatment using descriptive summary statistics for each treatment period. Moreover, percentage changes from baseline and follow ups respectively will be displayed.

The confirmatory inferential statistical evaluation of the primary outcome measure will be based on a linear mixed effects model with the Berg Balance Scale as dependent variable. This model will use the treatment group and period as fixed factor and the first baseline Berg Balance Scale as covariate. Random patient effects will be introduced for the intercepts and thus taking the correlation within patients into account.

ottobock.	CLINICAL INVESTIGATION PLAN	Document number:	PD-PS00120016A-001
		Version number:	7
Project name	Clinical trial comparing C-Brace to KAFO/SCO	Project no.	PS00120016A

The confirmatory analysis of the primary efficacy endpoint will be done for the intention-to-treat population. Additional efficacy analyses will be conducted for the per-protocol population. The p-values of these analyses will be interpreted in the exploratory sense only.

10.3.1 Secondary outcome analysis

Analyses for the secondary outcome measures will be performed for the intention-to-treat population as well as for the per-protocol population. All inferential analyses for the secondary efficacy variables will be interpreted in the exploratory sense. All secondary outcome measures will be evaluated by using descriptive statistics primarily, absolute values at each time point and if appropriate changes from first baseline and follow ups respectively. These analyses will be performed in a similar way as the primary efficacy outcome using a linear mixed effects model when appropriate.

Additional attention will be paid to the exploration of the measurements of safety and falls. The number of Falls is expected to be reduced in general by using a C-Brace, but the extent of a possible reduction remains uncertain. Therefore, frequency of falls, severity of falls, fall-related injuries, fear of falling and related treatment efforts will be explored in rigorously in order to formulate appropriate hypothesis for future research.

In the past the reduced probability of falling more than once by using C-Brace compared to KAFO / SCO showed the most promise as a reliable measure to compare the two device types, since it was less sensitive to outliers e.g. patients with a high number of falls on either device as compared to the total number of falls. However, sample sizes in prior research were relatively small and estimations for potential differences remain uncertain, albeit of great clinical interest.

Therefore, we explore whether a reduction in the probability of falling more than once using the C-Brace can be detected by a McNemar Test for paired proportions. This test will likely be underpowered in comparison to the expected best-case scenario used in the sample size calculation and will be reported accordingly.

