10.1.2 Secondary endpoints

An improvement in patients balance is hypothesized to aid the patients in their daily life and potentially influence some of the other outcome measures collected in this study. These measures will be explored without a strict expectation for the magnitude of expected change. Due to the expected nature of the distribution of the number of falls or rather the proportion of patients to fall more than once with the device C-Brace, these measurements would require the largest sample size in order to detect significant improvements at a reasonable power level.

If the probability to fall more than once with the device C-Brace is significantly lower than the probability to fall more than once with the device KAFO/SCO it could be used as a supporting argument to relevance of a potentially identified improvement in the primary efficacy endpoint. Previous observations on the RIC combination data however revealed a low expectancy of the probabilities to fall more than once with either KAFO/SCO and C-Brace device during the observed time span. A probability to fall more than once of $P_{KAFO/SCO} = 0.1333$ with the device C-Brace and a probability to fall more

ottobock.	CLINICAL INVESTIGATION PLAN	Document number:	PD-PS00120016A-001
		Version number:	7
Project name	Clinical trial comparing C-Brace to KAFO/SCO	Project no.	PS00120016A

than once of $p_{C-Brace} = 0$ for the device KAFO/SCO was recorded for 15 paired observations in the RIC combination study.

The sample size needed to detect a difference of $p_{diff} = p_{KAFO/SCO} - p_{C-Brace} = 0.1333$ for the paired proportions with on the basis of one-sided McNemar's Z-test without continuity correction is calculated as

$$n = \left(\frac{z_{1-\alpha} \sqrt{p_{disc}} + z_{1-\beta} \sqrt{p_{disc} - p_{diff}^2}}{p_{diff}} \right)^2$$

where $p_{disc} = p_{KAFO/SCO} + p_{C-Brace} = 0.1333$

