At a significance level of 0.05 and a power of 0.8, a total of 44.2386 of patients would be needed. Under the assumption of a dropout rate of 20% a total of 56 patients would need to be recruited. We recognize that the inclusion of a continuity correction may be more appropriate given the small proportion to fall more than once with either type of device and that a shift in the expected proportions away from zero would drastically increase the number of patients needed to detect the difference to show a significant difference. Regardless the merit of the observing these proportions at a higher absolute occurrence will yield a sound basis for future studies. For this reason, the number of patients to be included in the study is based on this value.

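### The exploratory McNemar test on falling more than once ignores period and randomised order; a period-adjusted version costs little and guards against bias if completion differs by sequence

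*Combined protocol and SAP*

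**What the plan says.** Section 10.3.1 (Secondary outcome analysis) states that "we explore whether a reduction in the probability of falling more than once using the C-Brace can be detected by a McNemar Test for paired" outcomes. It does not mention period or sequence, does not give the sidedness, and does not say whether the test is exact, continuity-corrected or uncorrected. The same section makes all secondary inference exploratory and expects this test to be underpowered. It extends the primary mixed model to secondary outcomes only where suitable.

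Section 10.3.2 (Primary efficacy outcome) treats the BBS differently: "This model will use the treatment group and period as fixed factor and the first baseline Berg Balance Scale as covariate".

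Section 10.1.2 sizes the trial on the fall endpoint. The words introducing the formula are "one-sided McNemar's Z-test without continuity correction is calculated as". The result is "At a significance level of 0.05 and a power of 0.8, a total of 44.2386 of patients would be needed", and then "Under the assumption of a dropout rate of 20% a total of 56 patients would need to be recruited". That section also says a significant fall result could support the relevance of a BBS gain, and that a continuity correction may be more suitable.

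Three other provisions bear on the point. Only the C-Brace-first sequence has the 4-week washout (7.3.8). Dropouts are replaced with no rule by sequence (9.3.3). Randomisation is by site in blocks of 6 (10.3.2, Randomization procedure).

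**The concern.** McNemar's test treats each discordant patient as a fair coin toss between devices. In a two-period crossover that holds under identical devices only if there is no period effect or if the two sequences are the same size. Otherwise part of a time trend in repeat falls is credited to one device.

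Neither condition is guaranteed here. Training before each home-use phase, monthly calls about falls and COVID-19 restarts could change fall risk between periods. Dropout, replacement without regard to sequence and a longer C-Brace-first path could leave unequal completion. At stake is a secondary result, but it is the one that sets the number of patients and that may be cited to show that a BBS gain matters. The randomised order needed to remove a period effect is already recorded.

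**Working it through.** **Inputs from the plan.** One-sided alpha 0.05, power 0.80, "p_{diff} = p_{KAFO/SCO} - p_{C-Brace} = 0.1333", "p_{disc} = p_{KAFO/SCO} + p_{C-Brace} = 0.1333", 20% dropout, 56 patients, blocks of 6 within site, nine sites.

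**Assumptions.** The plan gives no repeat-fall rates by period and no dropout by sequence. I use period-1/period-2 rates p1/p2 of 0.20/0.10 and 0.25/0.05, periods independent within patient, identical devices, and 45 completers (56 × 0.8 = 44.8). Splits are written KAFO/SCO-first/C-Brace-first.

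**1. The plan's figure.** n = [(1.6449 × √0.1333 + 0.8416 × √(0.1333 − 0.1333²)) / 0.1333]² = [(0.6006 + 0.2861) / 0.1333]² = 44.24, and 44.2386 / 0.8 = 55.30, rounded up to 56. Both figures reproduce.

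**2. Where the bias comes from.** Let a and b be the probabilities of repeat falls in period 1 only and in period 2 only, so a − b = p1 − p2. In the KAFO/SCO-first sequence a period-1-only patient counts against KAFO/SCO; in the C-Brace-first sequence the same patient counts against C-Brace. Hence, with identical devices,

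E[KAFO/SCO-only − C-Brace-only pairs] = (n_KAFO-first − n_CBrace-first) × (p1 − p2).

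Dividing by the number of completers gives the spurious risk difference:
- 26/19 at 0.20/0.10: 7 × 0.10 / 45 = 0.016.
- 27/18 at 0.25/0.05: 9 × 0.20 / 45 = 0.040, against a planned effect of 0.1333.

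**3. False-positive rate for a C-Brace benefit at a given split.** Exact enumeration of discordant counts, with a = 0.20 × 0.90 = 0.18 and b = 0.10 × 0.80 = 0.08, or a = 0.25 × 0.95 = 0.2375 and b = 0.05 × 0.75 = 0.0375.

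| Split | Period rates | Uncorrected Z | Exact McNemar |
|---|---|---|---|
| 23/22 | 0.20/0.10 | 0.052 | 0.026 |
| 23/22 | 0.25/0.05 | 0.045 | 0.022 |
| 26/19 | 0.20/0.10 | 0.073 | 0.038 |
| 26/19 | 0.25/0.05 | 0.090 | 0.049 |
| 27/18 | 0.20/0.10 | 0.081 | 0.043 |
| 27/18 | 0.25/0.05 | 0.111 | 0.063 |
| 28/17 | 0.25/0.05 | 0.136 | 0.079 |

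The direction reverses with the split. At 17/28 and 0.25/0.05, a false C-Brace benefit has probability 0.008 and a false KAFO/SCO benefit 0.136 (uncorrected).

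**4. How likely such splits are.** Simulated: 56 patients over nine equally recruiting sites, blocks of 6, independent dropout.

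| Dropout (KAFO/SCO-first / C-Brace-first) | P(gap ≥ 5, more KAFO/SCO-first) | Average error, uncorrected | Average error, exact |
|---|---|---|---|
| 20% / 20% (plan's rate, equal by sequence) | about 0.13 | 0.04–0.05 | at most 0.025 |
| 10% / 30% (assumed) | about 0.61 | 0.07–0.085 | at most 0.05 |

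Under equal dropout a gap of 5 or more in either direction has probability about 0.25. Favourable and unfavourable imbalances cancel on average, although the error at any one realised split does not.

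**5. Cost of adjusting.** Power at the planning rates (0.1333 against 0), Prescott against McNemar:
- 23/22: 0.95 against 0.95 asymptotic; 0.74 against 0.73 exact.
- 27/18: 0.90 against 0.95 asymptotic; 0.70 against 0.73 exact.

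The 0.95 exceeds the planned 0.80 because at these rates every discordant pair favours C-Brace, and three such pairs already exceed the critical value (√3 = 1.73). With no device effect, Prescott's test stayed at 0.043 to 0.055 (asymptotic) and at or below 0.031 (exact) in simulations over these kinds of split.

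**The case against.** The strongest reply has four parts.

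- **No overall inflation on the plan's own figure.** The plan assumes 20% dropout and no difference by sequence. Averaged over the resulting imbalance, the uncorrected test holds 0.04 to 0.05. This stands. The 10%/30% split is my assumption.
- **The liberal version is not what the analysis section specifies.** Only the sample-size formula is uncorrected. The exact test stays at or below 0.063 up to 27/18. This also stands, and it is a reason to name the version.
- **The endpoint is exploratory and period rates are not in the plan.** Correct; a fall from 0.25 to 0.05 on identical devices is large.
- **Intention-to-treat imputation could restore near-equal sequences.** Possibly, but section 10.2 gives no method for a binary fall outcome, and one of its two model descriptions omits period.

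A reader might infer that the planned test has an inflated type I error, or that it favours C-Brace. The documents support neither. Inflation needs a period effect and unequal completion together, no data in the plan show that either will occur, and the bias can equally hide a real reduction.

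**Conclusion.** The gap is real but conditional. The fall test omits a period adjustment that the plan makes for the BBS, and if both conditions arise the test and the risk difference are biased by an amount that can be written down in advance. At splits of 26/19 to 27/18 under the assumed period rates, the one-sided error is about 0.07 to 0.11 uncorrected and 0.04 to 0.06 exact. Averaged over equal 20% dropout it is not inflated; under an assumed 10%/30% dropout it is about 0.07 to 0.085 uncorrected and at most 0.05 exact.

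The confirmatory BBS analysis is not affected. It would be wrong to conclude that the fall result is invalid as planned. The case for changing it is that the protection is nearly free and the result may be cited in support of the primary finding.

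**What to change.** In section 10.3.1 (Secondary outcome analysis):

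1. Make Prescott's test the inferential analysis, or at least pre-specify it beside McNemar. Score each patient's fell-more-than-once indicator as period 1 minus period 2 (−1, 0 or +1), compare the scores between the two randomised sequences, and take the exact p-value from permuting sequence labels.
2. Report discordant pairs separately by sequence.
3. Estimate the device risk difference as the equally weighted average of the two within-sequence differences. With device effect δ and an additive period effect π these have expectations δ + π and δ − π, so the average is δ whatever the split.
4. State the sidedness and whether the exact or uncorrected version is used, and how a missing fall outcome is handled.

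Settle this before fall data are examined by sequence. The cost is a few sentences, no new data, and a small power loss when completion is unequal (0.90 against 0.95 asymptotic at 27/18; none at 23/22). A period-adjusted test built on discordant pairs alone (Mainland-Gart) would cost far more: power of about 0.37 exact or 0.51 mid-p at 23/22. Prescott's test removes a period effect only; it does not correct for carry-over or for dropout related to falls.
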